The trial will involve 6 CADCs across the sites; 3 CADCs (2 from OSLC and 1 from CLA) will be randomly selected to deliver CM+ and the other 3 CADCs (2 from OSLC and 1 from CLA) will deliver standard family-based CM. Based on our experience with RCTs, we anticipate turnover and have planned for as-needed recruitment of new CADCs and case re-assignment to ensure cases remain within condition. To ensure high fidelity and reduce confounding variables (e.g., access, insurance), the study will pay for treatment in both conditions, and investigators will train and closely monitor CADC staff.

Adolescents presenting to OSLC and CLA for SUD treatment during Study Months 7-42 will be screened, and those meeting inclusion criteria will be offered the opportunity to participate pending available slots. Power calculations (presented subsequently) indicate an optimal sample size of 172. Given case flow at the clinics, and our desire to oversample Latino families, we anticipate achieving the required sample size in 3 years. Specifically, CLA treats 23 adolescents with SUD per year on average, and all of these will be approached to participate in

the trial. Assuming an 80% recruitment rate (see subsequent rationale for this rate), we expect to recruit 55 families from CLA across the 3 years. OSLC serves just over 100 cases/year on average, so case flow will provide more than enough families to recruit the remainder of the sample (49/year x 3 years = 117). Based on information from OSLC and CLA, the following demographic characteristics are expected for youth recruited across both clinics: average age = 15 years (range = 12-17 years); 84% White, 13% African American, 2% American Indian/Alaska Native, 1% Asian; 35% Latino (of any race); and 30% female.

PARTICIPANTS

Participants will include 172 youth and their primary parent/guardian. Inclusion criteria for the youth are: 1) age 12-17 years; 2) presence of current SUD; and 3) availability of a parent/guardian willing to participate. Exclusion criteria are: 1) actively psychotic, suicidal, or homicidal; and 2) PDD or mental retardation. To increase external validity, youth will be included regardless of co-morbid mental health or physical difficulties.

RESEARCH SCREENING, RECRUITMENT, AND RETENTION

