Further, therapist implementation of interventions will be measured from the perspective of the youth, parent, and therapists (via self-report) and [name] and [name] (via coding of taped treatment sessions and PDR calls). As noted, the 34-item CM Adherence Measure (CAM) was developed using Rasch methods and validated across several studies. 166 CAM subscales measure the cognitive behavioral and behavioral interventions used in CM. Using the same format, items will be created to capture PMTO enhancements in CM+. Using standard procedures employed in our other CM studies, parents and youth will complete CAMs monthly by phone (for duration of treatment) to report on therapist's CM implementation. Investigators will monitor CAMs monthly for ongoing quality assurance and as-needed therapist remediation. In addition, a more immediate fidelity assessment and remediation mechanism will be therapists completing CAMs after each session and phone call to report on their own behavior. Further, therapists will record all treatment sessions and phone calls. [name] and [name] will complete observational ratings 167,193 on randomly selected (20%) treatment sessions and (20%) calls. Employing procedures used successfully in Azrin et al. 129 to monitor and improve fidelity, ratings will be compared to therapist report from the same session/call. Inconsistencies between therapist self-report and observational ratings will trigger remediation training and more intensive supervision. Session/call notes and reports also will be evaluated weekly to ensure fidelity across conditions.

BALANCING THERAPIST CHARACTERISTICS ACROSS CONDITIONS. We anticipate that 3 therapists will deliver CM, and 3 different therapists will deliver CM+. Prior to beginning youth recruitment, therapists will be randomized to provide services in either the CM or CM+ conditions. To minimize bias, therapists will be balanced as much as possible, given the small sample, by age, sex, race, and years of experience.

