EXPERIMENTAL MEDIATION AND CAUSAL INFERENCE. The experimental mediation design emphasizes evidence supporting causal inferences, and there are important conceptual and statistical considerations. As reviewed by [name], ¹⁹⁹ by randomizing youth/parents, the effect of CM+ on parent management is a causal estimate. However, the effect of parent management on drug use and externalizing behavior is not straightforwardly causal, it is potentially influenced by unmeasured confounding variables. Following [name]'s

recommendations, and to support causal inferences, this is addressed in 3 ways. First, the enhancement design directly targets the mediator—increasing probability of a causal effect between mediator and outcome. Second, longitudinal measurements of the mediator and outcomes address temporal sequencing—demonstrating that mediator effects occur before outcome effects. Third, supplemental models evaluate confounding variables—providing evidence that mediator effects are not due to confounders.

MODEL FORMULATION. The underlying model is a mixed-effects latent growth curve model with repeated measurements (level-1) nested within youth/parents (level-2), implemented in Mplus (v7.31;¹⁹⁷). As reviewed by [name],²⁰⁰ there are several options for modeling longitudinal mediation. Flexibility of growth models for targeting phase-specific change²⁰¹ are leveraged and combined with parallel process models for mediation.²⁰² In a single model, there are separate change estimates for during- and post-treatment phases, directly addressing temporal sequencing of mediators and outcomes. The UDS outcome is modeled using a Bernoulli distribution, and remaining ultimate outcomes, direct targets, and indirect targets are modeled with normal distributions. Time terms are computed using assessment dates.²⁰³ Treatment condition is a youth/parent-level predictor (level-2; CM = 0, CM+ = 1), and cross-level interactions are specified between condition and level-1 growth and phase terms. Models, as indicated, control for age, sex, race, ethnicity, SES, and treatment history. Likewise, preliminary models test, and control, for differences in outcomes across therapists and clinics. Follow-up models determine whether individual paths and mediated effects differ for males and females.

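### Therapists are fully nested in condition (3 vs 3 planned), yet the plan does not say when or how therapist differences will be controlled, and the power section describes no therapist clustering

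*Combined protocol and SAP*

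**What the plan says.** **Delivery.** Study Sites plans six counselors, three per condition, with two from OSLC and one from CLA in each arm. Addressing Risk of Contamination confirms that no therapist works in both conditions. Departures are provided for: "we anticipate turnover and have planned for as-needed recruitment of new CADCs and case re-assignment to ensure cases remain within condition". Under Balancing Therapist Characteristics Across Conditions, "Prior to beginning youth recruitment, therapists will be randomized to provide services in either the CM or CM+ conditions", and "therapists will be balanced as much as possible, given the small sample, by age, sex, race, and years of experience".

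**Analysis.** Model Formulation states: "The underlying model is a mixed-effects latent growth curve model with repeated measurements (level-1) nested within youth/parents (level-2"). Condition is a predictor at the family level. The one analytic sentence on therapists is "Likewise, preliminary models test, and control, for differences in outcomes across therapists and clinics". The a-path, b-path and mediation-test descriptions contain no therapist term.

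**Power.** Statistical Power for Mediated Effects describes a Mplus simulation with 155 families and R² = .07 on each path. It reports a-path power above .90, b-path power .85 and mediated-effect power .83. The inputs named are path coefficients, variances and residuals; no therapist ICC, design effect or therapist count appears. Study Sites rests the sample size on this: "Power calculations (presented subsequently) indicate an optimal sample size of 172".

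**The concern.** Families are randomized individually, but condition varies only between therapists. If families of the same therapist have correlated parenting trajectories, a family-level standard error for the CM+ effect is too small. The information on that effect then depends on the number of therapists as well as the number of families.

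The therapist sentence can be read in several ways, and they behave differently: control only after a significant preliminary test, a random effect referred to z, fixed therapist effects, or (least faithful to the wording) no therapist term in the final model. An analyst could choose among them after seeing the data.

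At stake is the a-path, the effect of CM+ on parent management. The plan calls it a causal estimate because families are randomized. Its coefficient and standard error go into the product-of-coefficients tests of Aims 1 and 2, so an understated standard error carries into those intervals. The preliminary c-path contrast has the same problem.

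**Working it through.** **Inputs.** From the documents: 172 randomized; 155 analysed (172 × 0.90 = 154.8); R² = .07; 6 therapists. Two-sided .05 is inferred from the 95% intervals. Assumed: equal allocation, equal caseloads, and a therapist ICC of .01/.02/.05/.10 for the during-treatment slope.

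**1. The plan's own figure.** f² = .07/.93 = .0753. Noncentrality λ = √(155 × .0753) = 3.416. Power = Φ(3.416 − 1.96) = .93 (noncentral F on 1 and 153 df: .92). The stated a-path power above .90 reproduces for independent families.

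**2. The same effect with therapist clustering.** Families per therapist m = 155/6 = 25.8. Design effect DE = 1 + (m − 1) × ICC. Power is taken at λ/√DE from the normal or the noncentral t distribution. Six therapists less two arms leaves 4 df, or 3 df if clinic is also a fixed term. Twelve therapists represent heavy turnover (m = 155/12 = 12.9).

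| Assumed ICC | 0 | .01 | .02 | .05 | .10 |
|---|---|---|---|---|---|
| DE, 6 therapists | 1.00 | 1.25 | 1.50 | 2.24 | 3.48 |
| λ/√DE | 3.42 | 3.06 | 2.79 | 2.28 | 1.83 |
| Power, normal | .93 | .86 | .80 | .63 | .45 |
| Power, 4 df | .73 | .64 | .56 | .41 | .29 |
| Power, 3 df | .63 | .55 | .48 | .35 | .25 |
| Power, 12 therapists, 10 df | .87 | .83 | .79 | .68 | .55 |

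**3. Fixed therapist effects.** Condition equals the sum of the CM+ therapists' indicators. Six indicators plus condition make 7 columns of rank 6, so the CM+ effect is not estimable. Clinic is different: both arms run at both clinics, so a clinic term can be fitted.

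**4. Type I error of the estimable readings.** Simulation with a true null a-path, 400,000 replicates per ICC, 6 therapists × 26 families (or 12 × 13), no clinic term. The pre-test is the nested F test at .05 on 4 and 6 × 25 = 150 df. If it is negative, the pooled family-level test is used; if positive, the 4-df test. The small-sample rule uses 4 df when the estimated therapist variance is positive and the pooled test otherwise. The row with therapist left out is 2Φ(−1.96/√DE).

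| Assumed ICC | .01 | .02 | .05 | .10 |
|---|---|---|---|---|
| Pre-test detects therapist variance | .11 | .18 | .40 | .65 |
| Type I error, pre-test reading | .07 | .09 | .12 | .12 |
| Random effect referred to z | .06 | .07 | .09 | .11 |
| Therapist left out | .08 | .11 | .19 | .29 |
| Random effect, small-sample df | .04 | .05 | .05 | .05 |
| Pre-test, 12 therapists | .06 | .07 | .08 | .08 |
| z, 12 therapists | .05 | .06 | .07 | .08 |

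With six therapists the preliminary test usually misses a small variance, so a non-significant result is no ground for dropping the term.

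**5. Other paths.** The b-path, and the Aim 3 a-path (parenting slope on behavioral-regulation and peer slopes), are not arm contrasts. In a simple single-mediator simulation, b-path power moved only from .92 to .90 as the ICC rose from 0 to .10. That simple model does not reproduce the stated .85 (it gives .91 to .92) or, by the Sobel method, the stated .83 (.69 to .71). It therefore supports the direction only, and no revised mediated-effect figure is offered.

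**The case against.** **Therapists are already controlled for.** The sentence can be read as testing and controlling unconditionally. On that reading, with a random effect referred to z, error is only .06 at ICC .01, and .05 with 12 therapists. That stands: the pre-test figures belong to one reading. But the text does not choose, and one natural form of control cannot be fitted.

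**Therapists are randomized and balanced.** This answers systematic bias. A reader might infer that the CM+ effect is biased by therapist allocation; the documents do not support that. The issue is understated variance and chance imbalance with few therapists.

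**The therapist variance may be close to zero.** Common training, weekly supervision, adherence monitoring and coding of sampled sessions (Achieving and Assessing Fidelity) are meant to limit it. The evidence for a material ICC is indirect: the contamination section says that fidelity varies between therapists, which is not a parenting slope, and the transportability study that found clinician effects on outcomes concerned another intervention. This stands as a limit on size. It does not establish zero.

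**Six is a planned count.** Turnover may add therapists, which eases the problem without removing it.

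**The stated power is wrong.** A reader might infer this, or work back from .85 and .83 to a precise loss. Neither follows. The growth-model parameters are not reported, and the section does not say which aim the .85 and .83 describe, so they cannot be assumed to form one chain with the arm contrast.

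**Conclusion.** The concern holds for the condition effects: the a-path of Aims 1 and 2, the c-path, and the mediated effects that use that a-path. The nesting is complete, and the plan gives no trigger, form or reference distribution for therapist control. This is more than missing detail. Some permitted readings exceed the nominal error rate at modest therapist variance, and one leaves the CM+ effect non-estimable.

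The sizes are illustrative, since they rest on an assumed ICC, equal caseloads and a two-mean approximation to the growth model. Type I error is about .07 to .12 (pre-test) or .06 to .11 (z) with 6 therapists, and .06 to .08 or .05 to .08 with 12. The a-path power of .93 becomes .86 to .45 on a normal reference with 6 therapists, and is lower on therapist-level df. The exact loss under the plan's own model, and whether .85 and .83 change, cannot be derived from the documents. Confidence is high in the gap and its direction, not in the amount. It should be fixed.

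**What to change.** Replace the therapist sentence in Model Formulation with a rule along these lines:

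1. Therapist enters every condition-effect model (a-path during-treatment slope; c-path outcome terms) as a random effect, or through a small-sample cluster method, whatever a preliminary test shows. Therapist is not entered as fixed effects; clinic is a fixed term.
2. The condition effect is referred to a named small-sample distribution, for example Satterthwaite-type or therapist-level df, allowing for the clinic term.
3. Re-assigned cases are analysed by first assigned therapist.
4. The therapist-adjusted a-path standard error is the one used in the product-of-coefficients interval.

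In the power section, rerun the Mplus simulation over a stated range of ICCs (for example .01 to .05) and therapist numbers (for example 6 to 12), and restate a-path and mediated-effect power for Aims 1 and 2.

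The cost is SAP text and a simulation rerun. No extra participants or data are needed, since the plan already intends to compare therapists. The downside is less favourable stated power, and a therapist variance estimated imprecisely from few therapists.

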CONCLUSION. The team has extensive experience evaluating and transporting EBPs. Our research suggests that while family-based CM is a well-validated EBP for adolescent SUD, its effects, like other adolescent SUD EBPs, are modest. Thus, this study will use an experimental mediation approach to identify mediating processes in treatment, with the ultimate aim of improving SUD treatment effectiveness. Backed by our experience conducting mediation and clinical studies, this study is poised to produce crosscutting implications for improving youth SUD treatments. Given the clear need to enhance effectiveness and durability of existing interventions, such work could have a dramatic impact on outcomes and services for youth.

DESIGN TIMELINE AND OVERVIEW

Data will be from a Ionaitudinal twoarmed parallel group design with 172 youth randomized to CM vs. CM+. In-person assessments will be at baseline, 2-, 4-, 6-, 9-, and 12-months postbaseline. Phone assessments will be at 1-, 3-, 5-, 7-, and 8months post-baseline.

STUDY SITES

The proposed study will be conducted with the OSLC outpatient clinic and Centro Latino Americano (CLA). Both are Medicaid-approved, HIPAA-compliant clinics employing Certified Alcohol and Drug Counselors (CADC) to deliver treatment services. While the two clinics serve all Lane County residents, CLA clients are predominantly Latino. As noted in the *Introduction*, adding CLA as a second site for this trial allows for oversampling of Latino youth, permitting an examination of differential mediation effects by ethnicity (see *Data Analysis*). Importantly, OSLC scientists regularly collaborate with OSLC clinic staff on intervention trials involving methods consistent with the proposed study. Similarly, OSLC scientists have a long history of collaborating with CLA on research and implementation projects. 149-150 Thus, the sites are optimal for ensuring adequate recruitment numbers, protocol fidelity, and successful completion of study procedures.

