An adaptive urn randomization procedure, ¹⁵⁵⁻¹⁵⁸ implemented using the Microsoft Access application gRand, will balance potential confounding variables among participants randomized to each condition and also will manage condition sizes. This method is recommended for trials of SUD treatments. ¹⁵⁵ Based on the population and outcomes of interest, factors on which the urn will operate are youth age, sex, baseline substance use severity, and a weighted percentage schedule for condition balance. The urn will minimize variability in these pre-treatment variables across the two conditions. To keep Assessors blind to condition, the Assessment Coordinator will conduct the randomization procedure immediately following a family's baseline assessment and will convey results directly to parents. The Coordinator also will inform the clinic intake worker of the randomization result so the family can be assigned to a CADC in the correct condition: CM+ or CM only.

DATA COLLECTION PROTOCOL

Assessors will meet with youth and parents for (1) a 2-hour, in-person baseline interview, (2) in-person, 1.5-hour follow-up assessments at 2-, 4-, 6-, 9-, and 12-months post baseline, and (3) 30-minute phone interviews at 1-, 3-, 5-, 7-, and 8-months. If youth and parent have to be assessed at different sessions, they will be scheduled within one week of each other. This schedule provides frequent measurement of constructs during active treatment (both CM+ and family-based CM are expected to last 5-6 months on average), while also providing a longer view on durability of change than is typical in adolescent SUD treatment research.¹⁹

To compensate for their time, families are paid \$50 for baseline and \$40 for each in-person follow-up assessment. Families will be paid \$10 for each brief telephone assessment (maximum total compensation = \$300). Based on our experience, 1.5- to 2-hour assessments rarely present a significant response burden, but Assessors are trained to use breaks with snacks and to attenuate circumstances that threaten validity of assessments. Participant protections are detailed in the Human Subjects Protocol and include IRB approval.

MEASURES

Multiple methods or perspectives will enhance construct validity. Consistent with intention-to-treat principles,

data from all time points will be collected even if families drop out of treatment.

Table 2. Research Instruments

Descriptive Variables [Baseline only]

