Structured Adolescent Interview¹⁵⁹ for demographics and to supply relevant data for the urn randomization.

Ultimate Outcomes [Months 0, 2, 4, 6, 9, & 12]

SUBSTANCE USE:

Urine samples collected by researchers from youth; lab testing for THC, synthetic THC, amphetamines, opiates, PCP, cocaine, and alcohol metabolites (EtG/EtS); selected lab's testing procedures are of high scientific quality.

GAIN¹⁵¹⁻¹⁵⁴ scales measuring self-reported youth substance use and substance-related problems; 16-item substance abuse index/substance dependence, substance problem scales assessing DSM-5 criteria for substance use disorders and lower severity symptoms, recovery environment risk and social risk subscales that predict substance-related problems in youth with substance abuse, and the substance frequency scale assessing substance use for past 90 days; GAIN scales have good reliabilities and sensitivity to change, and are highly associated with results from Form-90 and urine testing. ¹⁶⁰⁻¹⁶¹

EXTERNALIZING BEHAVIOR: Externalizing subscale of parent-completed **Child Behavioral Checklist** and corresponding subscale of **Youth Self Report**; ¹⁶² scales provide valid measures of youth externalizing behavior from multiple perspectives. ¹⁶³

Direct Target [Months 0, 1, 2, 3, 4, 5, 6, 7, 8, 9, & 12]

PARENT MANAGEMENT:

Alabama Parenting Questionnaire (APQ)¹⁶⁴ administered to youth and parents, measuring monitoring/supervision, positive parenting (social/tangible reinforcement), and consistent discipline (removal of privileges); scales have been used to document treatment outcomes and distinguish families of youth with and without behavior problems; ¹⁶⁴ scales have established reliability and validity; ¹⁶⁵ an additional rules and expectations subscale added to the APQ assesses enforcement of household rules.

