Early Adolescent Temperament Questionnaire–Revised^{172–173} completed by youth and parents; scales include inhibitory control and higher-order factors: effortful control, negative affect, affiliativeness, extraversion; good internal consistency.¹⁷³

Go/No Go Task of inhibitory control; youth selectively respond to target stimuli and inhibit responses to equally salient, non-target stimuli. 121,174 Consists of 252 trials: a letter is presented for 500-ms with a fixed, 1,500-ms interstimulus interval. Youth is instructed to press button as quickly as possible for every letter (go stimuli) except X (no go stimuli); 75% "go" trials and 25% "no go" trials; activates dorsolateral prefrontal cortex, ventral prefrontal cortex, and anterior cingulate cortex. 174 Consistent with prior research, 175–176 we will compute an index of inhibitory control: subtract percent correct on highly interfering stimuli ("no go" trials) from percent correct on minimally interfering stimuli ("go" trials). Lower scores indicate better inhibitory control.

TREATMENT CONDITIONS

FAMILY-BASED CM. Family-based CM is rooted in behavioral and cognitive behavioral theories and is designed for delivery in outpatient clinic settings (weekly 50-60 minute sessions). Treatment duration is criterion-based, determined by achievement of substance use goals, but the protocol is typically 5-6 months (20-24 sessions). CM has strong empirical support in the adult SUD treatment literature, ¹⁷⁷ and family-based CM has also proven efficacious for youth SUD. ^{13,178} Moreover, its relative simplicity and low cost ¹⁷⁹ makes family-based CM highly amenable to adoption. The protocol components are listed in Table 3.

Table 3. Family-Based CM Components

Clinical assessment. A semi-structured interview conducted separately with the youth and parent gathers type, frequency, quantity, and administration route of drug use; and data on treatment, medical, and educational history.

Introducing CM. CM is introduced to the youth and parent, and the therapist begins to engage them both in treatment.

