b-path. This model is more complex, simultaneously evaluating the mediator and outcome processes. To obtain this coefficient, the a-path is modeled along with the outcome model (c-path; testing for differences between CM+ and CM on substance use and externalizing behavior). With fewer outcome measurements, the model includes a during-treatment slope term and indicators to differentiate 9- and 12-month assessments, providing three estimates: during-treatment slope, change at 9 months, and change at 12 months. To obtain the b-path coefficient, a regression is specified with *during-treatment mediator slope* as a predictor of *outcome at 9 and 12 months*. This provides a targeted test of mediation, with during-treatment change in the mediator as a predictor of post-treatment outcomes.

Ethnicity effects. In close consultation with project consultant [name], and to address potential for differential effects across project clinics, formal moderated mediation tests can be performed.²⁰⁸⁻²⁰⁹ These tests determine whether observed mediation effects differ for Latino and non-Latino youth/parents. Sample size means that results are hypothesis-generating and thus will focus on estimation of confidence intervals. The same approach will be used to evaluate moderated mediation for ethnicity in Aims 2 and 3.

Confounding variables. Although randomization, the enhancement mediation design, and models addressing temporal sequencing increase the likelihood of valid causal inferences for mediation, a remaining assumption is that there are no unmeasured confounding variables for the mediator's effect. Cox et al.²¹⁰ recommends sensitivity analyses for confounder bias be used. First, VanderWeele's²¹¹ formulas identify youth/parents with the same value on the mediator but different values on the outcome, as well as youth/parents with the same value on the mediator across both CM and CM+ groups. Second, residuals from the models just detailed should be uncorrelated, and Mplus code from Imai et al.²¹² is used to determine whether the mediated effect differs based on unmeasured pre-treatment variables. Third, Mauro's²¹³ correlational method evaluates the sources of error variance from the mediation model, determining how large the effect of an omitted variable

would need to be to negate the mediated effect.

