AIM 2: DETERMINE WHETHER PARENT MANAGEMENT SKILLS (DIRECT TARGET) MEDIATE THE EFFECT OF TREATMENT ON YOUTH BEHAVIORAL REGULATION & DEVIANT PEER RELATIONS (INDIRECT TARGETS). In the parallel process model for Aim 2, the *a-path* is identical to that for Aim 1. The "outcome" model is nearly identical, the only difference being that the "outcomes" are indirect targets of treatment, behavioral regulation and peer relations. The b-path coefficient represents the association between the during-treatment slope for parent management and the 9- and 12-months post-treatment levels of behavioral regulation and peer relations.

AIM 3: DETERMINE WHETHER BEHAVIORAL REGULATION & DEVIANT PEER RELATIONS (INDIRECT TARGETS) MEDIATE THE EFFECT OF PARENT MANAGEMENT SKILLS (DIRECT TARGET) ON YOUTH SUBSTANCE USE & BEHAVIOR PROBLEMS (ULTIMATE OUTCOMES). Aim 3 uses the same approach, with one key difference: rather than treatment condition, the initial variable is parent management (the direct target of treatment) and, as such, there are repeated measurements. The *a-path* represents the effect of parent management on behavioral regulation and deviant peer relations. With both measured longitudinally, this takes the form of the during-treatment slope for parent management predicting the during-treatment slope for behavioral regulation and deviant peer relations. Although this could confound timing and sequencing of a-path effects, the results of Aim 2 will have established the extent to which there is evidence supporting a causal association between the direct and indirect targets of treatment. The outcome model is identical to that for Aim 1. The *b-path*, holding constant the effect of parent management, is the effect of the during-treatment slopes for behavioral regulation and peer relations on the post-treatment levels of substance use and behavior problems.

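### Aims 1-3 label fixed months 9 and 12 after baseline as post-treatment for every youth, although treatment length is open-ended and the month-9 GAIN frequency window opens at about month 6

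*Combined protocol and SAP*

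**What the plan says.** Outcome visits are counted from baseline. Design Timeline and Overview states: "In-person assessments will be at baseline, 2-, 4-, 6-, 9-, and 12-months postbaseline".

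Treatment end is not fixed. Under Treatment Conditions, Family-Based CM: "Treatment duration is criterion-based, determined by achievement of substance use goals", with 20-24 weekly sessions as typical. Data Collection Protocol adds that "both CM+ and family-based CM are expected to last 5-6 months on average". No maximum, spread or lag from baseline to first session is given. Randomization follows the baseline assessment, and assignment to a counselor comes after that.

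The two halves of the mediation model treat this differently:

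- **a-path (Aim 1).** The during- and post-treatment phases are set from each youth's own course of treatment, and post-treatment time is counted from treatment end.
- **Outcome model (Aim 1, b-path).** It has a during-treatment slope plus indicators for the 9- and 12-month visits. The regression is then described as a test "with during-treatment change in the mediator as a predictor of post-treatment outcomes".
- **Aims 2 and 3.** Both reuse this structure. Aim 2 refers to "the 9- and 12-months post-treatment levels of behavioral regulation and peer relations", and Aim 3 also speaks of post-treatment levels.

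Among the substance use measures, Table 2 lists "the substance frequency scale assessing substance use for past 90 days".

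**The concern.** Model Formulation says the separation of during- and post-treatment phases directly addresses temporal sequencing, and the section on causal inference relies on mediator effects preceding outcome effects. On the outcome side, nothing in the model checks that months 9 and 12 come after a given youth's treatment. Computing time from assessment dates does not help, because a visit date does not show whether treatment has ended.

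For a youth treated past about month 6, two things follow. The month-9 GAIN frequency score includes some use during treatment. Some parenting readings taken after month 6 (months 7 and 8, possibly 9) also count as during treatment, so mediator and outcome overlap in time. Because the stopping rule depends on substance use, this overlap would not fall on youth at random.

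What is at stake is the claim. A month-9 result could be reported as an effect after treatment, or as durability, when for some youth it is partly neither.

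**Working it through.** **1. The plan's own figures.** Sessions are "weekly 50-60 minute sessions". At 4 per month, 20/4 = 5.0 and 24/4 = 6.0 months, which reproduces the stated 5-6 months. At 4.35 weeks per calendar month the range is 20/4.35 = 4.6 to 24/4.35 = 5.5 months. The analysed sample is 172 × 0.9 = 154.8, stated as 155.

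**2. Where the visits fall.** With 5-6 months of treatment from baseline, month 9 is 9 − 6 = 3 to 9 − 5 = 4 months after treatment. Month 12 is 12 − 6 = 6 to 12 − 5 = 7 months after it. Neither is 9 or 12 months after treatment, as the Aim 2 wording would read literally.

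**3. Where the 90-day window opens.** With 30.44 days per month, month 9 is day 274. Then 274 − 90 = day 184, and 184/30.44 = month 6.04. The month-12 window opens in the same way at month 9.04. A youth who finishes by month 6 has a clean month-9 window, so the stated typical length clears it by 0 to 1 month.

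**4. How many might overlap.** The documents do not allow a single answer, so this is a range under assumptions. Let treatment end be T = L + D. L is the lag to first session (assumed 0, 0.5 or 1 month). D is gamma with mean m (5, 5.5 or 6) and SD s (0.5 to 2.5), so shape = (m/s)² and scale = s²/m. A month-9 GAIN frequency score overlaps treatment if T > 6.04. A youth is still in treatment at month 9 if T > 9.

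With no lag, P(T > 6.04) in percent, and P(T > 9) in brackets:

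| Mean | SD 0.5 | SD 1.0 | SD 1.5 | SD 2.0 | SD 2.5 |
|---|---|---|---|---|---|
| 5.0 | 2.3 (0.0) | 14.8 (0.0) | 22.6 (1.2) | 26.7 (4.0) | 28.9 (7.2) |
| 5.5 | 14.0 (0.0) | 27.9 (0.1) | 33.0 (2.0) | 35.1 (5.6) | 35.9 (9.2) |
| 6.0 | 45.5 (0.0) | 46.1 (0.4) | 45.5 (3.4) | 44.7 (7.9) | 43.8 (11.9) |

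With a lag, over the same means and SDs:

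| Lag | P(T > 6.04) | P(T > 9) |
|---|---|---|
| 0.5 month | 14-82% | 0-15% |
| 1 month | 43-98% | 0-20% |

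Of 155 youth, the no-lag range of 2.3% to 46.1% is about 4 to 71. Still in treatment at month 9 is 0 to about 19 (0.12 × 155) with no lag, and up to about 30 (0.195 × 155) with a one-month lag.

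These are shares with any overlap, not shares of the window. The 98% case has mean end 6 + 1 = 7.0 months and SD 0.5. Its average overlap is about 7.0 − 6.04 = 0.96 of 2.96 months, roughly a third of the window.

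**5. Which outcomes.** The 90-day argument applies to the GAIN frequency scale. Urine is sampled at the visit, and the balloon and Go/No Go tasks are done at the visit, so they are affected only if T exceeds about 9. The plan states no recall period for the externalizing, peer or temperament scales. The month-12 GAIN window overlaps only if T > 9.04, almost the same probability as T > 9.

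**The case against.** The case for the plan is fair on several points. At the stated typical length the month-9 window is clean, and no spread is given from which to show otherwise. The 90-day argument rests on one scale. The visit schedule is unambiguous elsewhere, so the Aim 2 phrase is a wording slip that would not change the coding. All of this stands and limits the point.

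It does not explain why the mediator's phase follows individual treatment end while the outcome's does not, and it supplies no rule for a youth still in treatment at month 9. The planned confounding analyses address omitted variables, not this.

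A reader might infer three stronger things that the documents do not support:

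- *That many or most month-9 scores are contaminated.* The range runs from a few percent to nearly all, depending on a spread and a lag that are not given.
- *That slow responders' use is held down by treatment at month 9 while early completers are off incentives, biasing the b-path in a known direction.* Table 2 (the adherence measure) and Table 3 (contingency contracting) intend parents to keep running contingencies at home, with measurement continuing after treatment ends. The contrast is therefore blurred. Every figure above measures overlap in time; none measures bias.
- *That the conclusion should move to month 12 alone.* That would discard month-9 outcomes that are post-treatment for youth who have finished, and month 12 is not wholly free of overlap either.

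**Conclusion.** The inconsistency holds and can be read from the text: the a-path uses each youth's treatment end, while the outcome model labels two fixed post-baseline visits as post-treatment for everyone. For any youth treated past about month 6 (GAIN frequency), or still in treatment at about month 9 (urine and tasks), the stated sequence of during-treatment mediator change followed by post-treatment outcome does not hold.

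How many youth this affects is unknown and possibly substantial. The 2-46% (GAIN frequency) and 0-12% (still in treatment at month 9) ranges rest on assumed gamma lengths with mean 5-6 months, SD 0.5-2.5 and no start lag, and both rise with a lag. No direction or size of bias in the b-path or the mediated effect is established. The point affects what may be called a post-treatment effect. It does not invalidate the fixed-time analysis.

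**What to change.** 1. In Aims 1-3, describe these outcomes as 9 and 12 months post-baseline. Keep both time points in the main analysis.
2. From the recorded treatment end dates, which the a-path already needs, report by arm the distribution of treatment length. Also report the share still in treatment, or within 90 days of its end, at months 9 and 12.
3. Add a sensitivity b-path using only outcomes whose assessment falls after that youth's treatment end. For GAIN frequency, the whole 90-day window must fall after it. If another scale has a recall period, state it and apply the same rule.
4. Fit month 12 alone as a supporting check.
5. Claim a post-treatment or durability effect only if these analyses agree with the main one.

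The cost is revised wording, one descriptive table and a little more analysis; no new data are needed. The sensitivity analysis will be less precise. It also uses a subset selected on a post-randomization event, so it supports the fixed-time analysis and does not replace it.
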